Using a randomized experimental design, 300 parents of 2-5 year old children (predominantly African American and economically disadvantaged) referred for behavior problems to the Family Center at Kennedy-Krieger Institute will be randomized to Parent-Child Interaction Therapy (PCIT; n=150) or Chicago Parent Program (CPP; n=150). Data on child behavior problems, parent discipline strategies, parenting self-efficacy, observed parent behavior, parent stress, and depression will be obtained from all participants at baseline and post-intervention assessments. Social risk will be assessed at intake. Parent satisfaction, attendance, and engagement in the intervention will be obtained at post-intervention. Clinical costs related to PT and non-PT treatment will be measured monthly. This innovative study will be the first to compare the effectiveness, cost, and social validity of a brief treatment designed with and for ethnic minority parents of young children against a well-established treatment considered to be the "gold standard." Determining whether a PT treatment can yield comparable effects for low-income, racial/ethnic minority parents of young children but at less cost, in less time, and with greater social validity is of significant public health importance.

2. Objectives: To compare the:

1. Effectiveness of PCIT and CPP for reducing behavior problems in a predominantly African American sample of children 2-5 years old from low-income communities. It is hypothesized that CPP will be equally as effective as PCIT for reducing child behavior problems based on parent report and observation.
2. Effectiveness of PCIT and CPP for improving parenting behavior and self-efficacy among a predominantly African American sample of parents of 2-5 year old children from low-income communities. It is hypothesized that CPP will be equally as effective as PCIT for improving parent discipline, self-efficacy, and observed parenting behavior.
3. Perceived social validity of PCIT and CPP based on parent satisfaction scores, treatment attendance, and parent engagement ratings (i.e., active parent participation in the intervention

Date: January 30, 2012
Principal Investigator: [name]
Application Number: NA_00039328

sessions). It is hypothesized that parents in the CPP condition will (a) attend a higher percent of PT sessions, (b) be more engaged, and (c) report higher satisfaction than parents in PCIT.

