b. Study duration and visits: Following consent, parents will be assigned to the appropriate block consisting of the next CPP group or the next available PCIT therapist. Participating parents and children will complete three assessment phases: baseline, 4 months post-baseline, and 9 months post-baseline. Each assessment phase includes parent-report surveys on child behavior problems, parenting self-efficacy, parent discipline strategies, stress, depressive symptoms, and attachment, and a 15- minute videotaped parent-child free play interaction (Dyadic Parent-Child Interaction Coding Systems; DPICS), followed by a clean-up session. Videotaped DPICS assessments will be coded by research colleagues at the University of Iowa ([name].) A Data Use Agreement will be obtained between Drs. [name], University of Iowa and [name], Johns Hopkins School of Nursing. Assessments typically require 45-75 minutes at each phase. All measures are described in Table 1 below.

Table 1. Parent-Child Variables, Measures, Informant, Items, Assessment Time-points*, Reliability, Validity

Variables	Measure(s)	Informant	# of Items	When Assessed	Reliability	Validity Evidence
Child Behavior Problems (parent)	Child Behavior Checklist (CBCL/1½-5) (Externalizing Scale & Internalizing Scale)	Parent	99	T1, T2, T3	.86-.89	[40; 41]
Child Behavior Problems (observed)	Dyadic Parent-Child Interaction Coding System (DPICS) (non-compliance, destructives, physical negatives, smart talk, cry, whine, yell)	Observer	7	T1, T2, T3	.73	[22; 57; 58]
Parent Self-Efficacy	Toddler Care Questionnaire (TCQ)	Parent	38	T1, T2, T3	>.93	[22; 57; 59; 60]
Parent Discipline	Parenting Questionnaire (PQ) (Warmth, Following Through, Corporal Punishment subscales)	Parent	50	T1, T2, T3	.68-.84	[22; 61]
Parent Depression	Center for Epidemiologic Studies Depression Scale-Revised	Parent	20	T1, T2, T3	>.85	
Parent Attachment	Attachment Style Questionnaire	Parent	40	T1	Test-retest .75-.80	
Parent Behavior	DPICS (Praise, Commands, Physical Coerciveness, Critical Statements, Positive/ Negative Affect)	Observer	10	T1, T2, T3	.88-.90	[22; 57; 58]
Social Validity: parent satisfaction w/ PT	Parent Satisfaction at end of program	Parent	4-12	T2 -CPP T3-PCIT	NA (items analyzed separately)	[34; 55; 57]
Social Validity: Degree to which parent actively participated in PT	Parent Engagement Scale	Clinician	7	T2-CPP T3-PCIT	.87	[35]

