- f. Definition of treatment failure or participant removal criteria: Participants will be removed from the study if they (a) lose custody of the target child during the course of treatment, (b) attend treatment sessions under the influence of drugs or alcohol, (c) become actively psychotic or aggressive during treatments, or (d) are uncooperative/noncompliant with the baseline research evaluation or with the

Date: January 30, 2012
Principal Investigator: [name]
Application Number: NA_00039328

Time 2 and Time 3 evaluations. Participants who are removed from the study for these reasons will still be eligible to receive all other treatments routinely available to them at the Family Center.

g. Description of what happens to participants receiving therapy when study ends or if participation in the study ends prematurely: Participants will remain eligible to receive all other treatments normally available to them at the Family Center.

5. Inclusion/Exclusion Criteria

Parent Inclusion criteria are (a) “parent” is the biological or adoptive parent or the legal guardian for the target child being treated at the Kennedy Krieger Institute, (b) parent is English- speaking, (c) child is 2-5 years old, (d) child is brought to the Family Center by the parent/legal guardian because of externalizing or internalizing behavior problems, and (e) willing to be randomly assigned to PCIT or CPP. There will also be 13 clinicians participating in this study and we expect all of them to be female.

Therapist inclusion criteria are (1) employed by the Family Center, (2) graduate-prepared licensed social worker, psychologist, professional counselor or equivalent, and (3) completed necessary training to provide PCIT or CPP

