Exclusion criteria are parent(s) who (a) has (have) severe mental illness that would interfere with their ability to participate in PT (measured by the Psychosis Subscale of the Basic-24 or diagnostic intake clinician assessment) and/or (b) is (are) actively using drugs or alcohol, based on clinician assessment at intake. Foster parents or relatives without legal status for the child are excluded since they may not be able to complete the study.. Children who are actively suicidal, psychotic, or who have significant developmental delay (i.e., fail developmental screening using Ages and Stages Questionnaire at intake), congenital, genetic, or sensory abnormalities that interfere with the child’s understanding, cooperation, and/or participation in PCIT or CPP will be excluded and referred for appropriate treatment services or hospitalization. Children diagnosed with autism or Pervasive Developmental Disorder will also be excluded since there is no evidence that CPP or PCIT is effective with these populations.

6. Drugs/ Substances/ Devices

- a. NA
- b. NA.
- c. NA

7. Study Statistics

- a. Primary outcome variables: Child behavior problems (parent report and observed from video recorded parent-child play/clean-up), parenting self-efficacy, parent discipline, parent behavior (observed from video recorded play/clean-up), parent satisfaction, parent engagement in the intervention, parent attendance in PT sessions.
- b. Secondary outcome variables: cost variables are those related to (1) time required to administer PT (including lost time for missed appointments) and additional non-PT therapy services used by parent or child (i.e., individual therapy, medications); (2) therapist time, (3) parent time, (4) childcare provided during CPP sessions; (5) space (including one-way mirror).
- c. Sample Size and Statistical Plan: Sample size in this equivalence study is designed to determine whether CPP is as effective as PCIT for the targeted clinical population (i.e., outcomes do not differ clinically or statistically). We used CBCL scores (child behavior problems) to estimate the sample size positing the null hypothesis that the absolute difference in the post intervention means between the CPP and PCIT groups will be > 0.5 standard deviations (i.e., > 5 point difference on the CBCL). The alternative hypothesis is that the absolute difference in the two means is less than or equal to 0.5

Date: January 30, 2012
Principal Investigator: [name]

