Application Number: NA_00039328

standard deviations. We will use the more conservative two-sided test. Thus, with 300 participants (150/condition) we will have 99% power to detect this difference using a two-sample comparison of means with alpha=0.05.

Hypothesis testing will mainly be conducted using repeated-measures MANOVA. Should the MANOVA be significant, univariate ANOVA will follow to identify the source of those differences. MANOVA was determined to be a more desirable approach than random regression models because MANOVA corrects for multiple tests of hypotheses. All baseline difference analyses and hypothesis testing will be conducted using 2-tailed tests and alpha =.05 (except tests to examine baseline differences between conditions, which will use .01 to correct for the multiple tests of hypotheses).

d. Early stoppage rules. Interventions will be discontinued if (a) more than 50% of parent participants in either condition report dissatisfaction on consumer satisfaction surveys with their assigned intervention or (b) more than 50% of child participants' CBCL scores (in either condition) worsen from baseline by $> .5$ SD. In this event, the research team will immediately convene with the members of the DSM committee to carefully review the protocol, reasons for dissatisfaction, and recommendations for change. A data safety and monitoring committee will meet early in the first year of the study to make additional recommendations for stoppage rules.

8. Risks

- a. Medical risks. Parent-Child Interaction Therapy and the Chicago Parent Program are psychosocial parent training interventions that have shown no evidence of medical risk. The major risks of this study are disclosure of confidential information and discomfort with the personal nature of some of the survey questions. These risks are no greater than what parents would be exposed to in a mental health treatment setting.
- b. Efforts to minimize risk. Efforts have been taken to minimize risk through appropriate training of research and clinical staff and the use of random number subject identifiers. All therapists have licensed and experienced therapists and have completed the appropriate training (PCIT or CPP).

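### The only reason given for preferring MANOVA, that it corrects for multiple testing, does not hold in general; the plan also leaves the handling of missed visits unstated

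*Combined protocol and SAP*

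**What the plan says.** Section 7c names repeated-measures MANOVA as the main method. The only argument against the alternative is that "MANOVA was determined to be a more desirable approach than random regression models because MANOVA corrects for multiple tests of hypotheses". The next step is: "Should the MANOVA be significant, univariate ANOVA will follow to identify the source of those differences". Hypothesis tests are two-tailed at .05. The one adjusted level, .01, is for baseline comparisons. The plan does not say which outcomes share a MANOVA and states no adjustment after or across MANOVAs.

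Section 7a lists eight primary constructs. Table 1 measures five of them at all three assessments: parent-reported and observed child behaviour, self-efficacy, discipline, and observed parent behaviour. The other three belong to Objective 3. Satisfaction and engagement are rated once (T2 for CPP, T3 for PCIT), and attendance is a percentage of sessions. For these a difference is predicted: "It is hypothesized that parents in the CPP condition will (a) attend a higher percent of PT sessions, (b) be more engaged", with higher satisfaction as the third part. The reliability entry for the 4-12 satisfaction items reads "NA (items analyzed separately".

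Objectives 1 and 2 are equivalence objectives. The sample-size null hypothesis is that the "absolute difference in the post intervention means between the CPP and PCIT groups will be > 0.5 standard deviations", equated with 5 CBCL points.

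On follow-up, section 4b says: "Participating parents and children will complete three assessment phases: baseline, 4 months post-baseline, and 9 months post-baseline". Section 4f(d) removes participants who "are uncooperative/noncompliant with the baseline research evaluation or with the" "Time 2 and Time 3 evaluations. Participants who are removed from the study for these reasons" remain eligible for the centre's other routine treatment. No analysis population, missing-data method or allowance for loss is given for this trial.

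**The concern.** The team considered random regression and set it aside for a property that MANOVA has only in part. A significant MANOVA used as a gate guards against false findings when nothing differs. Once one outcome really differs, the gate is very likely to open, and every remaining outcome is tested at .05. With two outcomes only one null test remains, so the error stays near 5%. From three outcomes upward it exceeds that. If instead each MANOVA holds one outcome with the visits as the multivariate response, there is no correction across outcomes at all. The stated reason fails in general on either reading.

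The rejected method also has an advantage. Repeated-measures MANOVA in its standard form drops any family without a full set of T1-T3 values on the outcomes entered. That is the usual behaviour of the method, not something the plan states, but the plan names nothing to offset it. A random regression (mixed) model uses every available visit. At stake are a false claim that the programmes differ on an outcome, and a comparison of selected families in place of the randomised groups.

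**Working it through.** **The plan's own figure.** Inputs from section 7c: 150 per arm, 0.5 SD, two-sided .05. SE = sqrt(2/150) = 0.1155 SD. Power = Phi(0.5/0.1155 - 1.96) = Phi(2.37) = 99.1%, which agrees with the stated 99%. That calculation is for a two-sample comparison of means, not for a MANOVA.

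**Error after the gate.** If the gate is sure to open and the p - 1 null outcomes are independent, the chance of at least one false difference is 1 - 0.95^(p-1):

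- p = 2: 5.0%
- p = 3: 1 - 0.9025 = 9.75%
- p = 5: 1 - 0.8145 = 18.5%

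Simulation relaxes both conditions. It used 3,000 runs, 150 per arm, an assumed T1-T3 correlation of 0.6, one outcome differing by 0.5 SD at T2 and T3, a Hotelling gate on all arm-by-time contrasts, then tests of T3 change at .05. Assumed between-outcome correlations were 0, 0.3 and 0.5.

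| Outcomes in the MANOVA | False difference among the others |
|---|---|
| 2 | 4.2, 5.3, 5.0% |
| 3 (Objective 2) | 8.8, 9.0, 9.6% |
| 5 (all repeated primary constructs) | 18.8, 18.2, 16.0% |

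Holm gave 4.2-5.3%. With no outcome differing, the gated procedure gave 2.5-4.1%, so it does protect there. A separate single-time simulation (20,000 runs) at correlation 0.7 gave 8.5% with three outcomes and 13% with five. With one MANOVA each for Objectives 1 and 2 (two and three outcomes), the error over both was 6.8-8.2% if the true difference lies in Objective 1 and 10.1-12.8% if it lies in Objective 2.

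**Families kept.** Let q be the assumed loss at each follow-up visit, with visits independent. Complete families number 300(1-q)^2; those with at least one follow-up number 300(1-q^2).

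- q = 0.10: 300 x 0.81 = 243, against 300 x 0.99 = 297
- q = 0.20: 300 x 0.64 = 192, against 300 x 0.96 = 288

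**Precision under random loss.** The SE of the arm difference in T3 change, complete-case against mixed model, is 0.1148/0.1072 (7% larger) at q = 0.10 and 0.1291/0.1121 (15% larger) at q = 0.20. At q = 0.30 the complete-case SE is 0.1475. Complete-case equivalence power with a 90% interval and a true difference of 0 is 2 x Phi(0.5/0.1291 - 1.645) - 1 = 97% at q = 0.20, and 92% at q = 0.30.

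**Bias under selective loss.** The simulation used 300,000 per arm, a true difference of 0, correlation 0.6, and logistic loss with slope 1 per SD in one or both arms. Arm-specific loss ran from 20% vs 10% to 36% vs 18%, and also 20% in both arms with differing mechanisms.

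- Loss driven by change to T2: complete-case bias 0.036-0.134 SD.
- Loss driven by baseline: 0.034-0.119 SD, with the opposite sign.
- Same rate and mechanism in both arms: at most 0.002 SD.
- Mixed model in all of these: at most 0.004 SD.
- Loss driven by the unseen T3 level: complete-case 0.032-0.122 SD, mixed model 0.047-0.171 SD.

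Since 0.5 SD is 5 CBCL points, 0.03-0.13 SD is 0.3-1.3 points.

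**The case against.** A MANOVA followed by ANOVAs is familiar practice. Objectives 1 and 2 predict no difference, which is the case where the gate works, and a false difference there would count against the trial's own hypothesis. This limits the harm but does not make the stated reason correct.

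Holm could equally follow the MANOVA, and a mixed model alone corrects nothing for multiplicity. That stands in full. The multiplicity argument supports adding an adjustment; the case for the mixed model rests on missed visits.

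A reader might carry the gate figures over to Objective 3, treating up to 12 satisfaction items plus attendance and engagement as 14 tests behind one MANOVA. The documents do not support that. These outcomes are not repeated measures, the items are noted as analysed separately, and section 7c says only that testing is mainly by MANOVA. What can be said is that no multiplicity adjustment is stated for them, although CPP is predicted to be better. A reader might also enter all eight primary constructs in one repeated-measures MANOVA, but only five are repeated.

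On missing data, listwise deletion is not written in the plan, and every loss rate, slope and correlation above is assumed. Gift cards, books and monitoring of retention should limit loss. The 36% attrition in the Background is stopping treatment in another PCIT study, not missed assessments here. Loss could differ by arm, because the 4-month assessment falls after CPP (3 months) but during PCIT (usually 6-8 months); the documents do not show that it will.

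**Conclusion.** The stated property of MANOVA is wrong as written. The planned sequence controls false differences when no outcome differs or when two outcomes are entered. With one true difference of 0.5 SD the error is about 9-10% with three outcomes and 16-19% with five (between-outcome correlation 0 to 0.5), against about 5% with Holm. With one outcome per MANOVA there is no correction across outcomes. It would go too far to say that MANOVA never protects.

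The missing-data point is secondary and conditional. If the standard form is used, and if loss depends on observed scores and differs by arm, the bias is about 0.03-0.13 SD in either direction at correlation 0.6. It is about 0 if loss matches across arms. A reader might infer that the trial would be underpowered, or that a mixed model removes attrition bias. Neither follows: equivalence power stays at 92-97% at 20-30% loss per visit, and the mixed model can be slightly worse when loss follows the unseen T3 level. The change should be made, but this does not by itself invalidate the trial.

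**What to change.** - Delete the stated reason for preferring MANOVA.
- Make the random regression (mixed) model the main analysis of the repeated outcomes, with all randomised families as assigned and all available T1-T3 data.
- For Objectives 1 and 2, judge equivalence by the confidence interval for the arm difference against the 0.5 SD margin. State the interval level, and whether the CBCL margin applies to the other outcomes.
- Apply Holm or a fixed order to any claim of difference, including Objective 3.
- Add a sensitivity analysis for loss that depends on unseen scores.
- Clarify section 4f(d): whether one missed evaluation leads to removal, and whether data already collected stay in the analysis. The removal rule itself is for the investigators.

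The cost is some extra analysis work and lower power for difference claims. At an assumed 0.3 SD and 150 per arm, power is Phi(0.3/0.1155 - 1.96) = 74% at .05, against Phi(0.3/0.1155 - 2.394) = 58% at Holm's first step with three tests (.05/3 = .0167). Equivalence power is kept with complete data and a true difference of 0: 2 x Phi(0.5/0.1155 - 1.645) - 1 = 99.3% with a 90% interval, and 98.2% with a 95% interval.
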